3.8 Safety Analysis

Safety assessments include AEs, clinical laboratory evaluations (hematology and chemistry), vital sign measurements, and electrocardiograms. Unscheduled visits for safety assessments will not be presented in by visit summary tables but will be in listings and shift tables. All safety analyses will be performed using the safety population.

3.8.1 Adverse Events

AEs will be coded using the MedDRA dictionary (Version 24.1 or higher). Treatment-emergent AEs (TEAEs) are any AEs occurring or worsening in severity after the first administration of study medication until 28 days after EOT. All AEs will undergo 4 sets of ratings by Investigator as follows:

- Serious vs. non-serious [based on seriousness criteria of death, life threatening, hospitalization – initial or prolonged, IME, disability or permanent damage, congenital anomaly or birth defects, and required intervention]
- Grades using the 5-point Common Terminology Criteria for Adverse Events (CTCAE 4.03) scale (mild, moderate, severe, life-threatening, or death)
- Causality assessment with respect to study drug classified as either: related (definitely related, related, probably related, and possibly related) or not related (unlikely related, not related).
- The relationship of AEs to cGVHD or the underlying disease

Kadmon Corporation

Page 20 of 26

The number (N) and percentage (%) of patients who experienced at least one TEAE will be summarized by dose group, including tabulation by:

- System Organ Class (SOC) and PT within each SOC in decreasing total frequency
- · Decreasing frequency of PT
- Maximum severity
- Relationship to study drug

These analyses will be repeated for serious TEAEs, events leading to dose modification, events leading to study drug discontinuation, events related to study drug and events related to cGVHD or the underlying disease.

Subject listings will be provided for AEs, SAEs, AEs resulting in study drug discontinuation and deaths. Time to onset and duration of AEs will be included in listings, along with action taken and outcome.

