## Disposition of Subjects

Overall, 64 subjects were screened for the study of whom 54 were included in the modified Intent-to-Treat (mITT) Population: 17 subjects in Cohort 1, 16 subjects in Cohort 2, and 21 subjects in Cohort 3. As of the cut-off date for this analysis (19 February 2020), 47 (87.0%) subjects have discontinued treatment and 7 (13.0%) subjects remain on treatment with

belumosudil. The most frequent reason for treatment discontinuation was disease progression (22 [40.7%] subjects). A total of 37 (68.5%) subjects were participating in the study, either being actively treated with belumosudil or being followed for survival (in Long-term Follow-Up). Seventeen (31.5%) subjects have discontinued from the study for the following reasons: 11 (20.4%) subjects died, 5 (9.3%) subjects were lost to follow-up, and 1 (1.9%) subject discontinued for other reasons. The overall median follow-up duration was 28.8 months: 35.9 months for Cohort 1; 32.4 months for Cohort 2; and 24.0 months for Cohort 3.

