# Disposition of Subjects

Overall, 132 subjects received at least 1 dose of belumosudil: 66 subjects in Arm A and 66 subjects in Arm B.

As of the cutoff date, 19 February 2020, the median follow-up duration was 7.9 months: 8.0 months for Arm A and 7.9 months for Arm B. In total, 62 (47.0%) subjects had discontinued from treatment; 70 (53.0%) remain on treatment with belumosudil. The most frequent reasons for treatment discontinuation were progression of cGVHD (16 [12.1%] subjects) and withdrawal by subject (14 [10.6%]). A total of 119 (90.2%) subjects participated in the study, either actively treated with belumosudil or followed for survival. Thirteen (9.8%) subjects had discontinued from the study: 8 (6.1%) subjects died; 3 (2.3%) subjects withdrew; 1 (0.8%) subject lost to follow-up; and 1 (0.8%) subject for which data was missing.

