### 9.9 Safety Analyses

Safety analyses will be performed on all subjects who receive at least one dose of belumosudil.

Adverse events will be coded using the Medical Dictionary of Regulatory Activities (MedDRA) (Version 24.0 or greater). The number and percentages of subjects experiencing TEAEs will be tabulated by System Organ Class and Preferred Term (PT). The number of events by PT will also be summarized. Tabulation by maximum severity and relationship to treatment will also be included by treatment group.

Summary subject listing will be provided for SAEs, AEs resulting in study discontinuation, and deaths.

Adverse events, SAEs, related AEs, related SAEs, Grade  $\geq$  3 AEs, related Grade  $\geq$  3 AEs, and AEs leading to withdrawal and treatment discontinuation, and deaths will be summarized.

Laboratory results will be summarized by treatment group, incidence of laboratory abnormalities, and worst on-study grade during the treatment period will be summarized. The incidence of Grade  $\geq$  3 laboratory abnormalities under treatment and shifts in toxicity grading from Baseline to highest grade post-baseline will be displayed.

Vital sign measurements and ECGs will be summarized by treatment group at each scheduled time point using descriptive statistics and included in data listings.

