3.6 Treatment Exposure

The number of subjects will be summarized, along with descriptive summary of duration of treatment, exposure ranges and overall exposure.

The duration of treatment (days) is defined as: (Date of last dose – Date of first dose) + 1. It will also be classified into the following exposure ranges: 0 to 6 months; > 6 to 12 months, > 12 to 18 months, > 18 to 24 months, > 24 to 30 months, > 30 to 36 months and > 36 months.

Overall exposure will be summarized in total patient-years, derived as Exposure in patient (years) = Sum of duration of treatment in days (for all patients in each dose group) / 365.25.

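### The SAP reports adverse events as crude percentages by dose group, with no exposure-adjusted rate or summary by time on drug, so risk and length of exposure are mixed

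*SAP*

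**What the plan says.** The study's single objective is long-term safety and efficacy (Protocol 2; SAP 2.1.1).

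- **Adverse event tables.** SAP 3.8.1: "The number (N) and percentage (%) of patients who experienced at least one TEAE will be summarized by dose group". The format is then extended: "These analyses will be repeated for serious TEAEs, events leading to dose modification, events leading to study drug discontinuation", and also to drug-related and disease-related events.
- **Timing of events.** SAP 3.8.1: "Time to onset and duration of AEs will be included in listings, along with action taken and outcome". Timing is not summarised.
- **Event counts.** Protocol 9.9 adds: "The number of events by PT will also be summarized". SAP 3.8.1 does not repeat this.
- **Person-time.** SAP 3.6: "Overall exposure will be summarized in total patient-years", derived for each dose group, with exposure bands from 0–6 months to over 36 months. SAP 3.3 splits disposition by exposure range. SAP 3.8.1 refers to neither.
- **Denominator.** SAP 3.2 runs all safety analyses on the Full Analysis Set, meaning everyone enrolled. SAP 3.8 names a safety population that SAP 3.2 does not define. Protocol 9.9 uses subjects with at least one dose.
- **Collection window.** Adverse events are collected from KD025-217 consent until 28 days after the last dose (Protocol Appendix A). Subjects who were already in long-term follow-up have contact assessments only (Protocol 6.2.2).

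**The concern.** A crude percentage compares groups fairly only when time at risk is similar. Here it runs from none, for those who enter off drug, to as much as two further years on top of unequal parent-study treatment.

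Two things are at stake. First, a dose group with longer exposure will show a higher percentage at the same underlying rate, and a group with many follow-up-only entrants will show a lower one. Second, no planned adverse event summary shows whether risk rises, falls or stays level with continued treatment. That is the main safety question an extension study can answer.

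**Working it through.** **No design figure to reproduce.** The plan states no power, alpha or target rate (Protocol 9.1 and 9.2; SAP 3.1.2). As a check on inputs, the parent-study percentages in Protocol Tables 2 and 4 were recomputed as n/N and agree. For serious events these are 23/54 = 42.6% and 45/132 = 34.1%. For Grade 3 or higher they are 33/54 = 61.1% and 65/132 = 49.2%.

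**Is time at risk unequal?** (Protocol 1.4.1 and 1.4.2, cut-off 19 February 2020)

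| | KD025-208 | KD025-213 |
|---|---|---|
| Median treatment, months | 8.4 (200 mg QD 8.5; 200 mg BID 7.5; 400 mg QD 9.0) | 6.7 in each arm |
| Treated more than 12 months | 42.6% | 6.1% |

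The medians are close, but the long-exposure tails are not, and extension subjects still on drug come from those tails. The two 200 mg groups pool both studies; 400 mg QD comes only from KD025-208.

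**Does it matter in the documents' own data?** Approximate rate per 100 patient-years = subjects with an event ÷ (N × median months) × 1200. The median stands in for the mean, which is not given, and time is not stopped at the first event. These figures are illustrations, not estimates.

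- Serious, KD025-208: 23 ÷ (54 × 8.4) × 1200 = 60.8. KD025-213: 45 ÷ (132 × 6.7) × 1200 = 61.1. The ratio goes from 1.25 crude to 1.00.
- Grade 3 or higher: 87.3 and 88.2. The ratio goes from 1.24 crude to 0.99.

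Serious events pooled by dose:

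| Dose | Crude | Person-months | Per 100 patient-years |
|---|---|---|---|
| 200 mg QD | 32/83 = 38.6% | 17 × 8.5 + 66 × 6.7 = 586.7 | 65.5 |
| 200 mg BID | 24/82 = 29.3% | 16 × 7.5 + 66 × 6.7 = 562.2 | 51.2 |
| 400 mg QD | 12/21 = 57.1% | 21 × 9.0 = 189.0 | 76.2 |

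The ratio of 400 mg QD to 200 mg QD goes from 1.48 to 1.16, and to 200 mg BID from 1.95 to 1.49. Within KD025-208 alone, 400 mg QD to 200 mg QD goes from 1.94 (57.1% against 5/17 = 29.4%) to 1.83 (76.2 against 41.5).

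**How far can exposure alone move a percentage?** With a constant rate h, the probability of at least one event by time t is 1 − exp(−h·t). The values of h are assumed.

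| h per 100 patient-years | 6 months | 12 months | 24 months |
|---|---|---|---|
| 10 | 4.9% | 9.5% | 18.1% |
| 30 | 13.9% | 25.9% | 45.1% |
| 60 | 25.9% | 45.1% | 69.9% |

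**Effect of the denominator.** If a share f of the Full Analysis Set entered off drug with no adverse event time, a true 50% among treated subjects prints as 50% × (1 − f). That is 45%, 35% or 25% for f = 10%, 30% or 50%. The documents do not give f.

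**The case against.** The strongest reply has four parts.

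1. **The plan holds more than percentages.** Protocol 9.9 counts events by preferred term, SAP 3.6 supplies patient-years by dose group, onset times are listed, laboratory, vital sign and ECG data are summarised by visit, and deaths enter the Kaplan-Meier analysis of overall survival. This stands in part, so it would be wrong to say that late risk cannot be seen at all. It does not close the gap. Counts by preferred term give no rate for serious or Grade 3 or higher events as a class. Total treatment time is not time to first event. The bands in SAP 3.6 beyond 24 months suggest that its patient-years include parent-study treatment, whereas adverse events are collected from KD025-217 consent, so dividing one by the other may mismatch numerator and denominator.

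2. **Follow-up is not time at risk.** A reader might compare "The overall median follow-up duration was 28.8 months" for KD025-208 with "the median follow-up duration was 7.9 months" for KD025-213 and infer a gap of that size between dose groups. The documents do not support this. Follow-up includes survival follow-up off drug, and 47 of the 54 KD025-208 subjects had stopped treatment. KD025-217 exposure by dose group is not given.

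3. **The study is descriptive.** There is no hypothesis, and the dose groups pool parent studies with different entry criteria, so dividing by person-time does not remove confounding. This stands, and it rules out a formal dose comparison.

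4. **The 400 mg QD group will be small.** Seven KD025-208 subjects, across all cohorts, were still on drug at the cut-off. Even if all seven were on 400 mg QD and treated for two more years (14 patient-years), one event would give an exact interval of about 0.2 to 40 per 100 patient-years. This also stands. The interval shows that imprecision, which a bare percentage hides.

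**Conclusion.** The point holds as an inexpensive improvement that should be made before the safety tables are programmed. SAP 3.8.1 pre-specifies no exposure-adjusted rate and no adverse event summary by time on drug. Unequal time at risk between subjects is documented; a difference between dose groups is a reasonable inference, not a documented fact.

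On size, the rough parent-study check removes the crude 25% excess of serious events in KD025-208 and shrinks the 400 mg QD to 200 mg QD excess from 48% to about 16%. Both results rest on medians used in place of means. Under an assumed constant 30 per 100 patient-years, going from 6 to 24 months on drug raises the percentage from 13.9% to 45.1% with no change in risk.

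A reader might go further and infer that the planned tables show length of exposure instead of risk, or that they will produce a dose difference of a particular size. Neither follows. Some of the dose difference remains after the rough adjustment, and within KD025-208 it barely moves (1.94 to 1.83).

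**What to change.** In SAP 3.8.1, next to the crude N (%):

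1. **Rates.** Report subjects with a first event per 100 patient-years at risk, with exact Poisson 95% intervals, by dose group and in total. Do this for serious, Grade 3 or higher, drug-related, discontinuation and fatal TEAEs and for common preferred terms.
2. **Time zero and end.** Count time at risk from the first KD025-217 dose to the first event, or otherwise to 28 days after the last dose. Adverse events are collected only from KD025-217 consent, and enrolled subjects had to survive to entry.
3. **Denominator.** Use subjects with at least one KD025-217 dose, so that follow-up-only entrants contribute no adverse event time. Reconcile Protocol 9.9, SAP 3.2 and SAP 3.8 accordingly.
4. **Time on drug.** For all dose groups combined, give Grade 3 or higher and serious rates by time since the first parent-study dose (0–12, >12–24, >24–36 and >36 months), with each subject entering at the KD025-217 start (delayed entry). This needs the parent-study first-dose date, which SAP 3.1.4 already uses, and no pooling of parent-study adverse events.
5. **Presentation.** Keep the rates descriptive, with no formal dose comparison.

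The cost is SAP wording and a few extra tables built from event and dosing dates that are already recorded, with no added burden on subjects or sites. The downside is wide intervals for the small 400 mg QD group.

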3.8.2 Clinical Laboratory Evaluation

The summary statistics (including number, mean, SD, median, minimum and maximum) of all laboratory variables and changes from baseline will be calculated for each visit or study assessment by treatment group.

For parameters of white blood cell counts, neutrophils (absolute count), lymphocytes (absolute count), monocytes (absolute count), hemoglobin, platelets, ALP, ALT, aspartate aminotransaminase, gamma glutamyl transferase, total bilirubin, glomerular filtration rate, plots of mean/mean changes from baseline with the corresponding standard error will be displayed.

For shift tables, laboratory results will be classified using the CTCAE 4.03. All graded laboratory parameters will be summarized separately for hematology and biochemistry. Corresponding shift tables to compare baseline to the worst post-baseline grade within the treatment period will be provided.

A by patient by lab tests by visit listing will be generated for lab results with CTC grade >=3.

The estimated glomerular filtration rate will be calculated and summarized using the Modification of Diet in Renal Disease (MDRD-4) and Chronic Kidney Disease Epidemiology Collaboration 2021 (CKD-EPI₂₀₂₁) methods. Below is the formula used for each respective method.

Kadmon Corporation

Page 21 of 26

Method	Formula
MDRD-4	eGFR = 175 x (S _{Cr}) ^{-1.154} x (age) ^{-0.203} x 0.742 [if female] x 1.212 [if Black]
CKD-EPI ₂₀₂₁	eGFR = 142 x min(S_{cr}/κ , 1) ^{α} x max(S_{cr}/κ , 1) ^{-1.200} x 0.9938 ^{Age} x 1.012 [if female]

Where:

Scr = standardized serum creatinine in mg/dL

 $\kappa = 0.7$ (females) or 0.9 (males)

 $\alpha = -0.241$ (female) or -0.302 (male)

min(Scr/κ, 1) is the minimum of Scr/κ or 1.0

max(Scr/κ, 1) is the maximum of Scr/κ or 1.0

3.8.3 Vital Signs

Descriptive statistics for vital signs (weight, temperature, systolic and diastolic blood pressure, pulse rate (beats/min), and respiratory rate (breath/min)) values and the change from baseline will be presented by treatment group for each scheduled assessment time point.

A by patient by visit listing will be generated for vital signs.

3.8.4 ECG

Descriptive statistics for ECG parameters (i.e., heart rate, PR interval, RR interval, QRS interval, QT interval, and QTcF interval) at each time point will be presented for the absolute values and change from baseline scores (QTcF is the QT interval using Fridericia's correction which is calculated by QTcF = QT/RR^{1/3}).

The number and percentage of subjects with observed absolute QTcF values at maximum value during treatment period that satisfy the following conditions will be presented by dose group: ≤ 450 ms; > 450 to 480 ms; > 480 to 500 ms; and > 500 ms.

The number and percentage of subjects having change from baseline QTcF at maximum value during treatment period that satisfy the following conditions will be presented by dose group: ≤ 0 ms; > 0 to ≤ 30 ms; > 30 to ≤ 60 ms; and > 60 ms.

A by patient by visit listing will be generated for ECG results.

Kadmon Corporation

Page 22 of 26

3.9 Pharmacokinetic Analysis

No PK assessments for analysis will be performed in this study.

3.10 Pharmacodynamics Analysis

No pharmacodynamic assessments for analysis will be performed in this study.

3.11 Exploratory Objectives Analysis

No exploratory analyses will be conducted.

4 APPENDIX A: Kadmon Algorithmic Response Assessments

Baseline Organ Involvement

Organ	Organ Involvement			
Esophagus	NIH Esophagus Score ≥ 1, not entirely explained by non-cGVHD			
	cause			
Upper GI	NIH Upper GI Score ≥ 1, not entirely explained by non-cGVHD cause			
Lower GI	NIH Lower GI Score ≥ 1, not entirely explained by non-cGVHD cause			
Lungs	FEV1 <75% predicted, not entirely explained by non-cGVHD cause			
	If no PFTs available, use NIH lung score ≥ 1, not entirely explained by			
	non-cGVHD cause			
Eyes	NIH Eye Score ≥ 1, not entirely explained by non-cGVHD cause			
Joints and	P-ROM Score <25 (< maximal score) or NIH Joints/Fascia Score ≥ 1,			
Fascia	not entirely explained by non-cGVHD cause			
Skin	NIH Skin Score ≥ 1, not entirely explained by non-cGVHD cause			
Mouth	NIH Modified Oral Mucosal Rating Score ≥ 1, not entirely explained by			
	non-cGVHD cause			
Liver	Elevation > 2x ULN of one or more (ALT, ALP, Total Bilirubin), not			
	entirely explained by non-cGVHD cause			

Response Assessments

Organ	Complete Response	Partial Response	Unchanged	Progression	Non Evaluable
Esophagus	NIH Esophagus Score 0 after previous involvement	Decrease in NIH Esophagus Score by 1 or more points	No change or increase from 0 to 1 in NIH Esophagus Score	Increase in NIH Esophagus Score by 1 or more points, except 0 to 1	NIH esophagus score is Non evaluable
Upper GI	NIH Upper GI Score 0 after previous involvement	Decrease in NIH Upper GI Score by 1 or more points	No change or increase from 0 to 1 in NIH Upper GI Score	Increase in Upper GI Score by 1 or more points, except 0 to 1	NIH upper GI score is Non evaluable
Lower GI	NIH Lower GI Score 0 after previous involvement	Decrease in NIH Lower GI Score by 1 or more points	No change or increase from 0 to 1 in NIH Lower GI Score	Increase in Lower GI Score by 1 or more points, except 0 to 1	If NIH Lower GI score is Non evaluable

Lungs	%FEV1 ≥ 80% after previous involvement; or NIH Lung Symptom Score 0 after previous involvement if PFTs not available	Increase by 10% absolute value of %FEV1; or decrease in NIH Lung Symptom Score by 1 or more points if PTSs not available	Not in the other categories	Decrease by 10% absolute value of %FEV1 and %FEV1 < 75%; or increase in NIH Lung Symptom Score by 1 or more points, except 0 to 1 if PFTs not available	NIH Lung score is Non evaluable and %FEV1 is missing
Eyes	NIH Eye Score 0 after previous involvement	Decrease in NIH Eye Score by 1 or more points	No change or increase from 0 to 1 in NIH Eye Score	Increase in NIH Eye Score by 1 or more points, except 0 to 1	NIH eye score is Non evaluable
Joints and Fascia	NIH Joint and Fascia Score 0 and P-ROM score 25 after previous involvement in at least one measure	Decrease in NIH Joint and Fascia Score by 1 or more points or increase in P-ROM score by 1 or more points for any site	Not in the other categories	Increase in NIH Joint and Fascia Score by 1 or more points or decrease in P-ROM score by 1 or more points for any site	Both in NIH Joint and Fascia and P-ROM scores are Non evaluable
Skin	NIH Skin Score 0 after previous involvement	Decrease in NIH Skin Score from baseline by 1 or more points	No change or increase from 0 to 1 in NIH Skin Score	Increase in NIH Skin Score from baseline by 1 or more points, except 0 to 1	NIH skin score is Non evaluable
Mouth	NIH Modified OMRS 0 after previous involvement	Decrease in NIH Modified Oral Mucosa Rating Score of 2 or more points	No change in NIH Modified Oral Mucosa Rating Score	Increase in NIH Modified Oral Mucosa Rating Score of 2 or more points	NIH mouth score is Non evaluable

Liver	Normal ALT, ALP and total bilirubin after elevation of one or more at baseline	50% improvement in ALT, ALP, or total bilirubin without increase by 2x ULN for any other parameters of ALT, ALP or total bilirubin	Not in the other categories	Increase by 2x ULN for any one of ALT, ALP or total bilirubin	If ALT, ALP and total bilirubin are missing
Global	GSR 0	GSR decreases by 2 or more points	Not in the other categories	GSR increases by 2 or more points	Not applicable

Organs not involved at baseline can progress according to the definitions in this Response Assessments table, but cannot achieve a response (PR or CR).

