# Appendix C: cGVHD Response Assessment

Response Determination for Chronic GVHD Clinical Trials based on Clinician Assessments

Organ	Complete Response	Partial Response	Progression
Skin	NIH Skin Score O after	Decrease in NIH Skin Score	Increase in NIH Skin Score by 1 or
	previous involvement	by 1 or more points	more points, except 0 to 1
Eyes	NIH Eye Score 0 after	Decrease in NIH Eye Score	Increase in NIH Eye Score by 1 or
	previous involvement	by 1 or more points	more points, except 0 to 1
Mouth	NIH Modified OMRS 0 after	Decrease in NIH Modified OMRS	Increase in NIH Modified OMRS
	previous involvement	of 2 or more points	of 2 or more points
Esophagus	NIH Esophagus Score 0 after	Decrease in NIH Esophagus	Increase in NIH Esophagus Score
10	previous involvement	Score by 1 or more points	by 1 or more points, except 0 to 1
Upper GI	NIH Upper GI Score 0 after	Decrease in NIH Upper GI	Increase in NIH Upper GI Score
	previous involvement	Score by 1 or more points	by 1 or more points, except 0 to 1
Lower GI	NIH Lower GI Score 0 after	Decrease in NIH Lower GI	Increase in NIH Lower GI Score by
	previous involvement	Score by 1 or more points	or more points, except from 0 to 1
Liver	Normal ALT, alkaline	Decrease by 50%	Increase by 2 × ULN
21701	phosphatase, and Total	Detrette by Don	increase by 2 × 02.
	bilirubin after previous		
	elevation of 1 or more		
Lungs	- Normal %FEV1 after	- Increase by 10% predicted	- Decrease by 10% predicted
Lungs	previous involvement	absolute value of %FEV1	absolute value of %FEV1
	- If PFTs not available, NIH	- If PFTs not available, decrease	If PFTs not available, increase in
	Lung Symptom Score 0	in NIH Lung Symptom Score	NIH Lung Symptom Score by 1
	after previous involvement	by 1 or more points	or more points, except 0 to 1
loints and fascia	Both NIH Joint and Fascia	Decrease in NIH Joint and Fascia	Increase in NIH Joint and Fascia
joints and fascia	Score 0 and P-ROM score	Score by 1 or more points or	Score by 1 or more points or
	25 after previous involvement	increase in P-ROM score by 1	decrease in P-ROM score by 1
Global	by at least 1 measure	point for any site	point for any site
Giodai	Clinician overall severity score 0	Clinician overall severity score	Clinician overall severity score
		decreases by 2 or more points	increases by 2 or more points
		on a 0-10 scale	on a 0-10 scale

ULN indicates upper limit of normal.

Source: Lee et al. 2015(25)

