3.7.2.7 Response by individual organ

For KD025-213 and KD025-217 organ involvement is captured in the CRF. For KD025-208, the database did not specifically capture baseline organ involvement. Organ involvement was determined as follows:

- All organs, except lungs:
 - If the baseline score is > 0, the organ will be defined as Involved, unless all response assessments are Not Evaluable (NE)
 - If the baseline score is 0, the organ will be defined as Not Involved, unless any response assessment of CR or PR which triggers clinical review to confirm baseline involvement.
- For the lungs:
 - If Forced Expiratory Volume in One Second (FEV1) ≥ 75%, the organ will be defined as Not Involved
 - o If FEV1 < 75%, the organ will be defined as Involved, unless all responses are NE

Kadmon Corporation

Page 18 of 26

The response assessment for the 9 individual organs (skin, eyes, mouth, esophagus, upper GI, lower GI, liver, lungs, and joints and fascia) and global severity rating is categorized into 5 response status: CR, PR, Progression, NE, Stable.

Number and percentage of subjects with best response of CR or PR and total (CR+PR) by individual organ system and global severity rating will be summarized and presented. With the total number of subjects in the Full Analysis Set with involvement of the given organ at baseline as denominator.

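### In subjects with liver involvement, the liver PR rule does not require the 50% improvement to be in a test that was raised at baseline

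*SAP*

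**What the plan says.** Four rules in SAP Appendix A act together on the liver.

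- **Involvement at baseline:** "Elevation > 2x ULN of one or more (ALT, ALP, Total Bilirubin"), provided a non-cGVHD cause does not fully explain it. One test is enough.
- **PR:** "50% improvement in ALT, ALP, or total bilirubin without increase by 2x ULN for any other parameters" of the three.
- **Complete response (CR):** "Normal ALT, ALP and total bilirubin after elevation of one or more at baseline".
- **Progression:** "Increase by 2x ULN for any one of ALT, ALP or total bilirubin".

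The closing line of the appendix adds that an organ not involved at baseline may progress, "but cannot achieve a response (PR or CR").

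SAP section 3.7.2.7 gives a second source for the involvement flag: "For KD025-213 and KD025-217 organ involvement is captured in the CRF".

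Protocol Appendix C asks only for "Decrease by 50" percent in its liver PR cell and names no test.

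Under SAP section 3.7.1, one improved organ with no progression in another is an overall PR, and ORR counts a CR or PR at any post-baseline assessment. Section 3.7.2.1 starts DOR at the first documented response.

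**The concern.** The involvement condition works on the organ, while the PR condition works on any single test. Once one raised test has qualified the liver, nothing in the PR cell stops a different, normal test from supplying the 50% fall. The CR cell next to it refers back to elevation at baseline; the PR cell does not.

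The response is computed by an algorithm. A programmer who follows the cell as written will code a liver PR for a subject whose abnormal test has not moved, or has worsened by less than 2x ULN. Such a PR enters the organ-level table directly. It reaches ORR and DOR when no other organ has progressed at that visit and the subject has no real response that already counts. Because the best response over all visits is used, each visit is another chance for ordinary laboratory variation to meet the rule.

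**Working it through.** The plan gives no figure on this point, so there is none to reproduce. The check has three parts.

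**1. The rules applied to test cases.** Values are in multiples of ULN. A rise by 2x ULN is read as a rise of two ULN units. ALT is 0.5 throughout. The last column requires the halved test to be above ULN at baseline.

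| Case | ALP | Bilirubin | As written | With the requirement |
|---|---|---|---|---|
| A | 0.6 to 0.6 | 0.8 to 0.4 | No response possible (not involved) | Same |
| B | 3 to 3 | 0.8 to 0.4 | PR | Unchanged |
| C | 3 to 4.5 | 0.8 to 0.4 | PR | Unchanged |
| D | 3 to 1.4 | 0.8 to 0.8 | PR | PR |
| E | 3 to 5.2 | 0.8 to 0.4 | Progression | Progression |

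Only B and C change. In C the rise is 4.5 - 3 = 1.5 ULN units, below the limit of 2. In E it is 5.2 - 3 = 2.2, so progression applies.

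**2. Chance of a 50% fall from variation alone.** The within-subject CV is not in the documents, so it is an assumption shown as a range. The model is log-normal with no true change. The log-scale SD is s = sqrt(ln(1 + CV^2)). At one visit the chance that follow-up divided by baseline is 0.5 or less is Phi(ln 0.5 / (sqrt(2) x s)).

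For CV 20%: s = sqrt(ln 1.04) = 0.198, and Phi(-0.693 / 0.280) = Phi(-2.47) = 0.7%.

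Visits are every 3 months (Protocol section 3.1) for up to 2 years, so 24 / 3 = 8. The 8-visit chances come from 400,000 simulated subjects with one shared baseline value per test. The two-test column treats the tests as independent.

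| Assumed CV | One visit, one normal test | Any of 8 visits, one normal test | Any of 8 visits, two normal tests |
|---|---|---|---|
| 10% | about 0 | about 0 | about 0 |
| 15% | 0.05% | 0.4% | 0.7% |
| 20% | 0.7% | 4.0% | 7.8% |
| 25% | 2.3% | 11.8% | 22.2% |
| 30% | 4.8% | 21.0% | 37.7% |
| 40% | 10.2% | 37.1% | 60.3% |

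These chances apply only to liver-involved subjects with a normal test at baseline. Subjects who stop early have fewer than 8 visits. If parent-study assessments also count as post-baseline, there are more.

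**3. Rough reach into ORR.** A subject changes category only if liver-involved, without a real response in any organ, and without progression elsewhere at the visit concerned. Protocol Table 1 (Study KD025-208) has 9 of 54 subjects (16.7%) with a best response of unchanged. Applied to about 70 subjects, this gives 70 x 9/54 = 11.7. The share with liver involvement is not given; 10-30% is assumed.

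- Low end (10% involved, CV 15%, one normal test): 11.7 x 0.10 x 0.0035 = 0.004 subject.
- High end (30% involved, CV 30%, one normal test): 11.7 x 0.30 x 0.21 = 0.7 subject, and 0.7/70 = 1 percentage point of ORR.
- High end with two normal tests: 11.7 x 0.30 x 0.377 = 1.3 subjects, or 1.9 points.
- Most generous, counting every lack-of-response subject (9 + 4 + 2 = 15 of 54, so 19.4 of 70): 19.4 x 0.30 x 0.377 = 2.2 subjects, or 3.1 points.

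The KD025-208 proportions may not carry over to this study, which enrols only subjects still on treatment or still free of a failure event.

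**The case against.** The best defence is the word used. The liver cell speaks of improvement, whereas the score-based PR cells and the protocol's liver cell speak of a decrease. A normal value that falls further has not clearly improved, and the neighbouring CR cell shows that the authors had baseline elevation in mind. This stands in part: the cell is unclear and does not expressly grant PR to a normal test. It does not remove the point, because a program needs one rule, two programmers could code this cell differently, and the protocol names no test that would settle it.

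A reader might infer that a subject with three normal liver tests could be called a responder. The documents do not support that: such a liver is not involved under Appendix A, and the closing line bars a response. A reader might also take 4-21% (CV 20-30%) as the error in ORR. It is the chance per normal test in a liver-involved subject under an assumed CV; it falls to 0.4% at CV 15% and to about zero at 10%. Nor can the cell be called wrong against the NIH 2014 consensus criteria from these documents, since only the protocol's short table is available.

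Two mitigations are real. Section 3.7.1 repeats ORR and DOR with the investigator's assessment of overall response, so a large gap would show. The study also tests no hypothesis, and its results are descriptive. Neither corrects the organ-level liver table. The clinical review in section 3.7.2.7 does not help either: it applies to KD025-208 organs with a baseline score of 0 and asks only whether the organ was involved.

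**Conclusion.** The point holds for subjects with liver involvement at baseline. As literally coded, the PR cell lets a normal test that halves give a liver PR while the raised test is unchanged or worse by less than 2x ULN. If no other organ progresses, the same event is an overall PR in ORR and can start DOR. This part rests on the text alone.

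The size rests on assumptions: no true change, a CV of 15-30%, and 8 visits. It is then about 0.4-21% per normal test in a liver-involved subject. The number of such subjects is not in the documents. On the rough figures above, the effect on ORR runs from almost nothing to about one percentage point on one normal test, and to about three on the most generous inputs. It is a minor point, worth correcting because the correction is cheap.

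**What to change.** Reword the liver PR cell in SAP Appendix A to say that at least one of ALT, ALP and total bilirubin that exceeded ULN at baseline must have improved by 50%, with no rise by 2x ULN in any other of the three. Program it that way.

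Use above ULN rather than above 2x ULN as the condition. The CR cell asks only for elevation, so a 2x ULN condition would make PR harder to enter than CR. For example, beside an ALP of 3x ULN, a bilirubin falling from 1.8x to 0.8x ULN (a fall of 1 - 0.8/1.8 = 56%) is a raised test that normalised, and a 2x ULN condition would deny it PR. It would also shut out a liver recorded as involved on the CRF with no test above 2x ULN.

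The cost is one phrase and a small change to the algorithm, using data already collected. The downside is slightly fewer liver PRs, and a small difference from any parent-study analysis that coded the cell literally. If results under the literal rule already exist, list the subjects whose response changes.
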